## 2. Synopsis

Anaemia is a global public health problem and is common in developing and developed countries, particularly among hospitalized patients. The World Health Organization defines anaemia as a haemoglobin concentration below 130 g/L in males and 120 g/L in females. A recent systematic review and meta-analysis on preoperative anaemia and outcomes after cardiac and non-cardiac surgery reported 39% of patients were admitted anaemic. These anaemic patients had three-fold higher odds of mortality, four-fold higher odds of acute kidney injury and twice the odds of infection. Not surprisingly, anaemia was also associated with increased transfusion, with anaemic patients five-times more likely to receive a red blood cell transfusion.

As these results indicate, red blood cell transfusions are often administered to correct low haemoglobin levels. However, correcting anaemia with transfusion is problematic as red blood cell transfusion has a dose-dependent association with increased mortality, morbidity, hospital and ICU length of stay, readmissions, and cost. Large risk-adjusted observational studies demonstrate that even transfusing a single unit of red blood cells is associated with increased adverse outcomes in surgical patients, thus recommending caution before transfusing.

In an attempt to find the “optimal” transfusion threshold, many randomized controlled trials have investigated the difference between using restrictive pre-transfusion haemoglobin thresholds compared with liberal pre-transfusion haemoglobin thresholds. A restrictive strategy refers to a policy of administering red blood cell transfusions at comparatively lower pre-defined haemoglobin levels, with the goal of minimizing the use of blood. Though not always the case, restrictive transfusion

thresholds are often defined as haemoglobin levels between 70 g/L and 80 g/L and liberal transfusion thresholds are commonly defined as haemoglobin levels between 90 g/L and 100 g/L.

A recent systematic review and meta-analysis published in the Cochrane Library concluded there is no difference in morbidity or mortality between restrictive and liberal transfusion strategies. However, these trials are often confounded by transfusions administered pre-randomization, a lack of comparable transfusion dosing regimens between studies, and at times small differences in actual mean pre-transfusion haemoglobin levels between control and intervention arms. In addition, these randomized controlled trials still leave many important questions unanswered. For example, are haemoglobin thresholds lower than 70 g/L just as effective as haemoglobin levels higher than 70 g/L? Some have suggested lower haemoglobin thresholds may be just as effective. Interestingly, lower thresholds are already applied in clinical practice in challenging patient populations.

Other studies have investigated mortality in patients with very low haemoglobin levels who do not receive red blood cell transfusions. These studies found that each 10 g/L decrease in haemoglobin below 80 g/L was associated with a 1.8 to 2.5 times increased odds of mortality, with sharper increases in mortality observed when the haemoglobin fell below 50 g/L. However, these studies do not address what effect red blood cell transfusion would have on outcomes at various nadir or pre-transfusion haemoglobin levels.

Additionally, while many studies have investigated the effect of anaemia on outcomes independent of red blood cell transfusion, and the effect of red blood cell transfusion on outcomes independent of anaemia, very few investigate if and how these two independent risk factors interact with each other.

The aim of this study is to determine what relationship red blood cell transfusion has with mortality and length of stay at various levels of nadir haemoglobin. To achieve this objective a retrospective observational study will be conducted, involving three hospitals from Western Australia. The study will include all elective and emergency surgical admissions over a 9 year period (July 2008 – June 2017).

### **3. Objectives**

The specific objectives addressed by the study are:

1. Is there an association between in-hospital mortality, 30-day mortality, and hospital length of stay and red blood cell transfusion at various levels of nadir haemoglobin?
2. Is there an effect modification between levels of nadir haemoglobin and presence of a red blood cell transfusion on in-hospital mortality, 30-day mortality, and length of stay?

### **4. Benefits**

This study proposal includes important strengths. First, it involves admissions over a 9 year period from three hospitals across the largest surgical specialties responsible for transfusion and therefore will provide a large sample size for analyses. Second, this study will be conducted in a health service with low mean pre-transfusion haemoglobin thresholds, indicating there are likely more transfused and non-transfused patients at comparatively lower nadir haemoglobin levels available for analyses. Given these two important characteristics this study will likely have more power to detect differences in outcomes between transfused and non-transfused patients at lower levels of haemoglobin than previously reported.

Third, while some studies have investigated the impact of nadir haemoglobin and transfusion on outcomes, they focused on specific patient groups. This study will focus on the major surgical groups responsible for the majority of red blood cell transfusion and thus will increase the generalizability of results to other tertiary hospitals.

Thus the results of this proposed study will make an important contribution to the current body of literature and may guide future decisions on what transfusion thresholds researchers select for randomized controlled trials, or whether these randomized trials are even asking the correct research questions.

## **5. Literature Review**

Rhode and colleagues pooled the results of 18 trials investigating what effect restrictive pre-transfusion haemoglobin thresholds have on hospital acquired infections. They found patients assigned to restrictive transfusion thresholds had a significantly lower risk of infection when compared to patients assigned to liberal transfusion thresholds (risk ratio 0.82, 95% CI 0.72 to 0.95). This significant risk reduction remained unchanged in a sub group analysis of trials using leukocyte reduced red blood cells.

Curley and colleagues conducted a systematic review and meta-analysis of randomized controlled trials comparing restrictive to liberal transfusion haemoglobin thresholds in patients undergoing cardiac or vascular surgery. In the pooled results from seven studies they report no statistically significant difference between the two groups in terms of mortality, length of stay or other outcomes. One limitation is the small difference in haemoglobin thresholds between the restrictive and liberal protocols studied, often a 10 g/L difference. The impact of this small difference is evident in the mean units of red cells transfused between groups, approximately half a unit, with patients in the liberal arm transfused a mean 1.9 red cell units and patients in the restrictive arm a mean of 1.4 units.

Docherty and colleagues also conducted a systematic review and meta-analysis looked at the effect of restrictive versus liberal transfusion strategies in patients with cardiovascular disease undergoing non-cardiac surgery. The main outcome investigated was 30-day mortality and cardiovascular events. The authors found no statistically significant difference in 30-day mortality between groups (risk ratio 1.15, 95% CI 0.88 to 1.50). However, there was a significant increased risk of acute coronary syndrome in patients assigned to a restrictive threshold when compared with patients assigned to a liberal transfusion threshold (risk ratio 1.78, 95% CI 1.18

to 2.70). As is common with other the other meta-analyses reviewed, one limitation of this review is the overlapping transfusion thresholds studied. Of the studies pooled the cut-off values for the restrictive transfusion thresholds ranged from 70 to 97 g/L, the cut-offs for the liberal transfusion thresholds ranged from 90 to 113 g/L.

The largest of these systematic reviews and meta-analyses to date is the study by Carson and colleagues published in the Cochrane Database of Systematic Reviews. The review's aim was to compare mortality and other outcomes in patients randomized to restrictive versus liberal red blood cell transfusion thresholds. The authors found no statistically significant difference in hospital mortality (risk ratio 0.86, 95% CI 0.73 to 1.01) or 30-day mortality (risk ratio 0.97, 95% CI 0.81 to 1.16), or any difference in the other outcomes measured. Hospital length of stay was recorded as part of the review, however the results were not included in the analysis. One of the limitations of this study is that the majority of randomized controlled trials pooled applied a restrictive transfusion threshold of 80 g/L or higher. In clinical practice many hospitals report lower mean pre-transfusion haemoglobin thresholds, and when applied with other strategies to appropriately manage a patient's own blood (referred to as Patient Blood Management) this is often associated with improved outcomes.

At face value, the results of the three systematic reviews and meta-analyses investigating mortality tell a consistent story: no significant difference in mortality when restrictive transfusion thresholds are applied compared with liberal transfusion thresholds. These results suggest hospitals adopting restrictive transfusion threshold policies would likely reduce transfusions, reducing patient exposure to transfusion risk, with no evidence of increased mortality.

However, another systematic review and meta-analysis investigated the impact of applying more restrictive pre-transfusion haemoglobin thresholds. Salpeter and colleagues pooled results from trials using a restrictive haemoglobin threshold of less than 70 g/L and compared the outcomes between the restrictive and liberal transfusion arms. They found that in trials applying a lower restrictive threshold (less than 70 g/L), patients assigned to the restrictive arm had significantly lower in-hospital mortality (risk ratio 0.74, 95% CI 0.60 to 0.92) and total mortality (risk ratio 0.80, 95% CI 0.65 to 0.98), when compared to liberal transfusion group. A separate analysis was conducted to study the outcomes in trials applying a higher "restrictive" transfusion threshold, between 75 g/L and 100 g/L. The authors found no significant difference in in-hospital mortality (risk ratio 0.65, 95% CI 0.37 to 1.15) or total mortality (risk ratio 1.03, 95% CI 0.81 to 1.31). This important difference may explain why some randomized controlled trials report reduced mortality with restrictive transfusion thresholds compared to liberal thresholds, while others report no significant difference.

Still these five systematic reviews and meta-analyses of randomized controlled trials leave important questions unanswered. While patients assigned to restrictive transfusion threshold arms are less likely to receive a transfusion the fact remains that among these trials nearly half of patients in the restrictive group still receive transfusions. In one meta-analysis 48% of the restrictive group were transfused compared with 84% in liberal group. Some have used the results from these trials to draw conclusions about whether red blood cell transfusions are harmful. However by design, results from these trials alone cannot be extrapolated to

describe the effect of transfusion versus no transfusion on mortality or other outcomes. Further limiting the interpretation of results is the fact that many large trials do not include all the units of blood transfused during hospital admission, as blood transfused prior to randomization is often overlooked.

Some observational studies in the surgical setting have sought to address this gap in the literature by comparing outcomes between patients transfused and those not transfused across various levels of anaemia. For example, in patients undergoing cardiac surgery, Shaw and colleagues used a propensity-matched analysis to compare the outcomes of patients transfused to those not transfused at four preoperative haematocrit levels (a measure of anaemia). They found that transfused patients had higher mortality rates than those not transfused, at all levels of haematocrit. Kougais and colleagues studied the impact of postoperative nadir haemoglobin levels and transfusion on outcomes in patients presenting for elective operations for atherosclerotic vascular occlusive disease at one hospital. They found that neither red blood cell transfusion nor nadir haemoglobin level was associated with the composite end point of death and/or myocardial infarction. Interestingly, there was no significant interaction between transfusion and nadir haemoglobin, suggesting transfusion had the same effect on outcome regardless of the nadir haemoglobin level.

While these studies provide some insights into differences between outcomes in transfused and non-transfused anaemic patients they also leave many unanswered questions. For example, what are the outcomes in patients with haemoglobin thresholds lower than 70 g/L?

Two case series have investigated mortality in patients with very low haemoglobin levels who do not receive red blood cell transfusions. These studies found that each 10 g/L decrease in haemoglobin below 80 g/L was associated with a 1.8 to 2.5 times increased odds of mortality, with sharper increases in mortality observed when the haemoglobin fell below 50 g/L. However, these studies do not address what effect red blood cell transfusion would have on outcomes at various nadir haemoglobin levels.

## **6. Research Plan**

### **6.1. Description of population and sample.**

This project will include all adults admitted as elective or emergency cases for selected surgical specialties to three hospitals in Western Australia between July 2008 and June 2017. Local studies show that the following six specialties account for the majority of blood transfused in surgical patients.

- Orthopaedics
- Gastrointestinal Surgery
- Vascular Surgery
- Urology
- Cardiothoracic surgery
- Neurosurgery

Any patients transfused fresh frozen plasma, platelets, and cryoprecipitate will be excluded from the study. This is to reduce the possibility of confounding as the purpose of this study is to focus on nadir haemoglobin levels, red blood cell transfusion and their effect of mortality and length of stay.

Also excluded are patients receiving a massive transfusion (defined as 5 units of red blood cells in 4 hours or 10 units in 24 hours), patients transfused any blood products 90 days prior to admission, patients with a length of stay of less than 2 days (same day and overnight admissions), patients under the age of 18 years at admission, and patients with no haemoglobin results.

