## **6.2. Description of data gathering methods, including definitions of variables.**

The majority of data needed for this project will be sourced from the *Western Australian Patient Blood Management System*. The advantages of sourcing the majority of data from one system include consistent data collection processes and classification of variables.

The exposure variables of interest are degree of anaemia and red blood cell transfusion. Anaemia will be defined using the nadir haemoglobin result during admission for those not transfused and the pre-transfusion haemoglobin result in patients transfused, as described previously. The pre-transfusion haemoglobin will be the closest level measured prior to the first red blood cell transfusion administered. Fridges are available for storing blood in theatres and because of this the timing of red blood cell transfusion in the operating room is unknown. Therefore for patients transfused in the operating room the nadir haemoglobin result will be used as a surrogate for the pre-transfusion haemoglobin result. Haemoglobin levels will be grouped into the following categories: below 50 g/L, 50-59 g/L, 60-69 g/L, 70-79 g/L, 80-89 g/L, 90-99 g/L, 100 g/L or over. These cutoffs were selected after reviewing similar studies.

The main outcome variables of interest are mortality and hospital length of stay of current admission. For the mortality analysis, both in-hospital and 30-day all-cause mortality will be assessed. In-hospital and 30-day mortality will be calculated from date of death recorded in hospital patient admission systems (TOPAS/WebPas). Potential confounders collected will include age at admission, sex, hospital, discharge year, admission type (emergency or elective), clinical specialty, and patient comorbidities.

Patient comorbidities will be assigned a score based on the Charlson Comorbidity Index derived from ICD-10 codes for the comorbidities identified. To ensure the Charlson score represents patient comorbidities on admission, hospital-acquired complications will be excluded from the calculation.

Other data items to be collected include admission date, discharge date, discharge specialty, diagnosis related group, hours in ICU, presence of a red blood cell transfusion (yes/no), had a massive transfusion (yes/no), and number of red blood cell units transfused.

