### **6.3. Validity and reliability of data**

The research methodology for this project is based on methodologies used in similar studies. To improve the validity of results, potential confounding variables will be statistically adjusted for in the analysis, and inpatients receiving transfusions other than red blood cells will be excluded.

This study will investigate consecutive adult surgical admissions to three public hospitals for specialties where blood is commonly transfused. Given the study design and the broad inclusion criteria applied, the results are expected to have external validity and are likely generalizable to other surgical inpatients admitted to large teaching hospitals internationally.

Exposure and outcome variables have been carefully selected and are known to be accurately measured. Results from laboratory testing will be used to measure nadir haemoglobin values to accurately define the degree of anaemia. The cut-offs for haemoglobin levels have been selected based on other studies.

The in-hospital and 30-day mortality outcome measures selected for this study are well-defined objective measures and will be coded as binary variables (yes/no). Hospital length of stay, also a frequently studied objective outcome measure will be calculated in days from admission to discharge. All outcomes variables will be measured in the same way between the different subgroups.

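### The exclusions for other blood products and massive transfusion select on events during the stay and fall unequally on the transfused group, so they cannot be assumed simply to reduce confounding

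*Protocol*

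**What the plan says.** Section 6.1 of the protocol sets two exclusions that depend on what happens in hospital. The first is "Any patients transfused fresh frozen plasma, platelets, and cryoprecipitate will be excluded from the study", with the reason "This is to reduce the possibility of confounding". The second, in the next paragraph and without a stated reason, is "patients receiving a massive transfusion (defined as 5 units of red blood cells in 4 hours or 10 units in 24 hours").

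The same paragraph also excludes "patients transfused any blood products 90 days prior to admission". That is the only transfusion exclusion with a time window, and the window closes before admission.

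Section 6.3 repeats the product rule as a measure to improve validity: "inpatients receiving transfusions other than red blood cells will be excluded". It then relies on broad inclusion criteria to expect results that carry over to surgical inpatients in large teaching hospitals internationally.

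Section 6.2 fixes the reference point for transfused patients: "The pre-transfusion haemoglobin will be the closest level measured prior to the first red blood cell transfusion administered". Patients transfused in theatre are the exception. The timing of their transfusion is unknown, so their nadir is used instead. Untransfused patients are also classified by the nadir of the admission. On adjustment, section 6.2 says: "Potential confounders collected will include age at admission, sex, hospital, discharge year, admission type (emergency or elective), clinical specialty, and patient comorbidities".

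**The concern.** Eligibility should not depend on events that can follow the exposure. A patient who receives one red cell unit, keeps bleeding and later needs plasma, or reaches the massive-transfusion limit, leaves the cohort because of that later course. A patient at the same haemoglobin whose bleeding stops stays in. If the patients removed have higher mortality and longer stays, and more of them come from the transfused group, the remaining transfused patients look better for reasons unrelated to any effect of transfusion.

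Both objectives in section 3 concern the association of transfusion with mortality and length of stay by haemoglobin level, so this selection acts directly on the main estimates. The covariates contain no measure of bleeding, coagulopathy or acute severity that could offset it.

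**Working it through.** **1. Timing, from the text.** The protocol states a window for earlier transfusion (90 days before admission) and none for the other two rules. Section 6.3 speaks of inpatients receiving other products. Both rules therefore cover the whole stay. Massive transfusion needs at least 5 units, so it is always reached after the first. Other products may come before, with or after the first unit.

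**2. Which group loses patients.** For massive transfusion, 100% of exclusions are transfused patients, by definition. For other products the split cannot be derived, because plasma or platelets can be given without red cells. As an illustration, take 65,000 admissions (the middle of the 60,000 to 70,000 in section 6.5). Assume 10% transfused, giving 6,500 transfused and 58,500 untransfused.

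- Transfused excluded, assumed 5% to 20%: 325 to 1,300.
- Untransfused excluded, assumed 0.5%: about 292. Transfused share of exclusions: 325/617 = 53% to 1,300/1,592 = 82%.
- Untransfused excluded, assumed 2%: 1,170. Transfused share: 325/1,495 = 22% to 1,300/2,470 = 53%.

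The transfused share of the head count is thus uncertain. It is the difference in exclusion rates between the groups (here 5% to 20% against 0 to 2%) that moves the odds ratio.

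**3. Effect on a crude odds ratio.** Assume mortality of 4% transfused and 1% untransfused. The starting odds ratio is (0.04/0.96)/(0.01/0.99) = 4.13. If a fraction f of a group with mortality m is excluded, and those excluded have r times the group's mortality, the remaining mortality is m(1 − f·r)/(1 − f).

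| f transfused | r | f untransfused | Mortality left, transfused | Mortality left, untransfused | Odds ratio |
|---|---|---|---|---|---|
| 5% | 2 | 2% | 3.79% | 0.98% | 3.98 |
| 10% | 2 | 0.5% | 3.56% | 0.99% | 3.67 |
| 10% | 3 | 0 | 3.11% | 1.00% | 3.18 |
| 20% | 3 | 0 | 2.00% | 1.00% | 2.02 |

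Over the full grid (f transfused 5%, 10%, 20%; r 2, 3; f untransfused 0, 0.5%, 2%) the odds ratio falls to between 0.97 and 0.49 of its starting value.

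**4. Selection alone, with no true effect.** A simulation of 4 million patients assigned red cells at random, with no effect on death. A latent severity U (standard normal) drives death, logit = −4 + U, and exclusion, logit = −2.5 + U in the transfused group. The full-cohort odds ratio was 1.00.

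| Excluded, transfused | Excluded, untransfused | Odds ratio after exclusion |
|---|---|---|
| 10.5% | 0 | 0.88 |
| 10.5% | 1.1% | 0.89 |
| 10.5% | 10.5% | 1.00 |

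In this model the shift comes from unequal exclusion; it vanishes when the rates are equal.

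**5. Why the net direction stays open.** Suppose mortality is 3% in everyone who remains, in both groups, and 8% or 12% in those excluded (5% to 20% of transfused, 1% of untransfused). With these patients kept, the odds ratio runs from 1.07 to 1.58. For example, at 20% and 12% the transfused mortality is 0.2 × 12% + 0.8 × 3% = 4.80% and the untransfused 0.01 × 12% + 0.99 × 3% = 3.09%, giving 1.58. After exclusion it is 1.00, but only because 3% was assumed for both. The same figures fit two accounts: a real association hidden by selection, or confounding by bleeding severity correctly removed. They cannot tell the two apart.

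The protocol gives no mortality, transfusion rate or exclusion count by group, so every rate in steps 2 to 5 is an assumption. The effect on length of stay was not quantified.

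**The case against.** Restricting to patients without other products is a recognisable design choice when the question is about red cells. Severe bleeding or coagulopathy causes both transfusion and death. With no severity covariate, keeping these patients adds confounding by indication. Even a product given later can mark a coagulopathy already present at the first unit. The simulated 0.88 to 0.89 needs random assignment, which this study does not have. All this stands, and it is why the net bias cannot be signed.

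Three stronger readings are tempting, and the documents do not support them.

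- *The rules remove the sickest patients almost only from the transfused group.* This exclusivity is certain for massive transfusion alone. For the other products there is no split, and no figure shows that those excluded are the sickest or are concentrated in the low haemoglobin bands.
- *A null result, or apparent benefit at low haemoglobin, would be the work of the exclusion.* The illustrations show that selection can push that way, not that it outweighs the opposing confounding.
- *The confounding rationale is simply wrong.* It is attached only to the product rule, and for products given before or with the first unit it may hold.

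A sensitivity analysis may also be left to the SAP, so its absence is not the point here. The point is an exclusion, a rationale and a generalisability statement that the protocol itself fixes. An SAP can compare the two cohorts only if these patients are in the extract, and receipt of other products is not among the data items listed in section 6.2, although it is needed to apply the rule.

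**Conclusion.** The point holds in limited form. Both exclusions rest on events at any time in the stay. Massive transfusion is always reached after exposure begins and removes transfused patients exclusively. The other-product rule probably removes them disproportionately, without figures to confirm it. Unequal, severity-related exclusion can lower the transfusion odds ratio: to 0.97 to 0.49 of its starting value in the assumed grid, and to 0.88 or 0.89 under the simulated null. It can also shorten length of stay in the transfused group.

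Because this works against residual confounding by bleeding severity, the documents do not allow the net bias to be signed, and the exclusions cannot be assumed simply to reduce confounding. The claim of broad applicability in section 6.3 also goes beyond a cohort from which these patients have been removed.

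**What to change.** 1. Keep the planned analysis unchanged.
2. Retain the excluded patients in the extract with flags. Massive transfusion (yes/no) is already listed in section 6.2. Add receipt of plasma, platelets or cryoprecipitate, with date where available.
3. Report the number excluded under each rule, and their deaths, by transfusion group and haemoglobin band.
4. Rerun the mortality and length-of-stay models with these patients retained, at minimum those with massive transfusion. Report both sets of results by band.
5. If the two sets differ, limit the conclusion and the generalisability statement in section 6.3 to surgical patients who received no other blood products and no massive transfusion.

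Excluding only patients whose other product preceded the haemoglobin that sets the band would not solve the problem. For untransfused and theatre patients that value is the nadir of the whole stay, so the rule would still select on in-hospital events, over different windows in the two groups.

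Cost: one or two extra fields and one rerun. The second analysis set is more heterogeneous and carries more confounding by indication, so it should be read beside the planned analysis, not in place of it.
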